A linear model will be fit (for all of the data or for a subset of histopathology values, depending on the findings from the plot) where the dependent variable is the vascuCAP™ measurement ( $X$ ) and the independent variable is the histopathology value ( $Y$ ). Generalized estimating equations (GEEs) (to account for the fact that some patients will have more than one target lesion) will be used to estimate the linear function:  $E(Y|X) = \beta_0 + \beta_1 X$ . An unstructured working covariance will be used. We will construct a 95% CI for the intercept  $\beta_0$  using a t-statistic as the pivotal statistic. CIs not containing 0 indicate fixed bias. We will also construct a 95% CI for the slope  $\beta_1$ . CIs not containing 1 indicate proportional bias [11].

The precision of the vascuCAP™ measurements will be estimated by the standard deviation:

$$\sqrt{\frac{1}{n-1} \sum_{i=1}^n (Y_i - X_i - \bar{d})^2} \text{ where } \bar{d} \text{ is the sample mean of the differences, } \bar{d} = \frac{1}{n} \sum_{i=1}^n (Y_i - X_i) \text{ [1].}$$

We will construct a 95% CI for the precision using bootstrap methods.

We will plot the bias profile (plot of bias of measurements for various ranges of histopathology values vs. the histopathology value) and precision profile (plot of standard deviation of vascuCAP™ measurements from patients with similar histopathology values vs. the histopathology value) as visual summaries of vascuCAP™ performance for the bias and precision components, respectively [12].

In addition to reporting these technical performance characteristics of the volume measurements, we will also report i) the coverage probability (CP) and ii) a discrimination index [11]. The CP is the probability that the absolute difference between the value measured by vascuCAP™ and the value measured by histology is less than  $d_0$ , i.e.  $\pi = \Pr(|Y - X| < d_0)$ . We will plot the CP for a range of values for  $d_0$ . The discrimination ability of the measurements, i.e. the ability of vascuCAP™ to discriminate between different magnitudes of histopathology values, will be measured using the area under the ROC curve for continuous measures [13]. 95% CIs for the CP and ROC area will be constructed using methods for clustered binary data [14] and clustered ROC data [15], respectively.

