The volume measurements are considered the most critical because they will be used to construct a score to predict rupture risk. Thus, we considered the width of 95% confidence intervals for the bias and the between-subject variance as a function of sample size (see Tables 1 and 2). The following assumptions were made: 1) the volume measurements are normally distributed; 2) carotid artery patients contribute one target lesion each, while PAD patients contribute two target lesions each; 3) target lesions from the same patient are moderately correlated ( $r=0.5$ ); 4) one-quarter of all patients will be PAD patients; 5) results from femoral and carotid target lesions can be pooled; 6) the average volume of an analyte is  $25\text{mm}^3$ ; and 6) the precision of the vascuCAP™ measurements is 10-20% of the volume of analyte.

From Table 4, if the SD was 15% of the mean volume, then we expect to be able to construct a 95% CI for the bias of total width of 10% with  $n=35$ . If the SD was 20%, then with  $n=35$  we expect to construct a 95% CI of total width of 14%. Similarly, from Table 5, if the SD was 15% of the mean volume, then with  $n=35$  we expect to be able to construct a 95% CI for the precision of total length 8%; if the SD was 20%, then we expect to be able to construct a 95% CI for the precision of total length 11%. We plan to recruit 75 patients (55 carotid artery patients and 20 PAD patients) in phase one to account for the fact that the estimates of bias and

precision may need to be reported in strata based on the magnitude of the histopathology volume and/or by anatomic location. In phase two we plan to recruit at least the minimum of 35 (25 carotid artery patients and 10 PAD patients) and possibly more depending on the results of the training set.

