**Table 5: Estimated 95% CIs for SD Based on Total Sample Size (n)\***

	n=10	n=20	n=30	n=40	n=50	n=60
SD=2.5	[1.80,4.77]	[1.98,3.81]	[2.08,3.51]	[2.11,3.29]	[2.16,3.20]	[2.19,3.14]
SD=3.75	[2.70,7.16]	[2.97,5.71]	[3.11,5.26]	[3.17,4.94]	[3.24,4.80]	[3.29,4.71]
SD=5.0	[3.60,9.54]	[3.96,7.61]	[4.15,7.02]	[4.22,6.59]	[4.31,6.40]	[4.38,6.29]

\*The effective sample size,  $m$ , is calculated as  $m=(3/4)n+(1/4)n(2/[1+(s-1)0.5])$ , where  $s=2$ .

Then the 95% CI for the SD is  $[\sqrt{\frac{(m-1)s^2}{\chi_{\frac{\alpha}{2},(m-1)}^2}}, \sqrt{\frac{(m-1)s^2}{\chi_{(1-\frac{\alpha}{2}), (m-1)}^2}}]$ .

For degree and uniformity measurements for each analyte for each site (i.e. neck and leg), we will tabulate the histopathology value vs. the vascuCAP™ value. Any analyte not measurable will also be indicated in the table. In the distributions in the tables are similar, then the data from the two sites will be pooled.

The coverage probability (CP) will be reported which is the probability that the absolute difference between the value measured by vascuCAP™ and the value measured by histology is less than  $d_0$ , i.e.  $\pi = \Pr(|Y - X| < d_0)$ . We will report the CP for values for  $d_0$  of 0 and 1. 95% CIs for the CP will be constructed using methods for clustered binary data [6].

For volume, degree, and uniformity of the six functional analytes, we will estimate the reproducibility of the measures at different institutions (two sites), and under different scanner models and field strengths (1.5 and 3.0) and with respect to ranges documented in the literature according to collected patient characteristics. Multiple variable linear and logistic regression models will be built, where the dependent variable is the difference between the measured functional analyte and the true value, and the independent variables are institution, scanner model, field strengths, and patient characteristics. We will test whether the independent variables in the model are predictors of bias using F-tests, and Wald tests, respectively.

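### The bootstrap 95% CI for precision is left unspecified, and the ordinary choices cover the true SD only about 89–91% of the time at the phase-two minimum of 35 patients

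*Combined protocol and SAP*

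**What the plan says.** Section 8.1 defines the estimand: "The precision of the vascuCAP™ measurements will be estimated by the standard deviation" of the paired differences, with an n−1 divisor over lesions. The interval gets one sentence: "We will construct a 95% CI for the precision using bootstrap methods". Nothing is said about the type of bootstrap, whether patients or lesions are resampled, or how many resamples are drawn.

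The sample-size argument in the same section uses a different interval. Table 5, headed "Estimated 95% CIs for SD Based on Total Sample Size", has a footnote beginning "Then the 95% CI for the SD is" and continuing with a chi-square interval that uses an effective sample size m. From that table the text expects total lengths at n=35 of 8% of mean volume (SD 15%) and 11% (SD 20%). The stated assumptions include that "the volume measurements are normally distributed", that "carotid artery patients contribute one target lesion each, while PAD patients contribute two target lesions each", and that "target lesions from the same patient are moderately correlated" (r=0.5).

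The phase-two minimum is 25 carotid and 10 PAD patients, and Section 4 allows up to 75 patients. Carotid and femoral data are pooled only if their plots look alike.

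**The concern.** In small samples a bootstrap distribution for an SD sits too low and is too narrow, so the usual intervals taken from it tend to be short and to miss on the low side. The planned samples are small enough for this to matter, and the text leaves the analyst free to pick the weakest variant.

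Precision is part of primary objective I. Section 4 makes phase two the source of the definitive 510(k) results, and Section 8.1 ranks the volume measurements as the most critical. An interval labelled 95% that falls below the true SD too often flatters the device. The expected lengths given for planning also belong to an interval that will not be reported.

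**Working it through.** **1. The plan's own figures (Table 5).** The footnote sets m = (3/4)n + (1/4)n × 2/(1 + 0.5), with limits SD × √[(m−1)/χ²] at the upper and lower 2.5% points on m−1 df.

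- At n=35, m = 26.25 + 8.75 × 1.333 = 37.92. The chi-square points on 36.92 df are 55.57 and 22.04.
- SD 3.75: 3.75 × √(36.92/55.57) = 3.06 and 3.75 × √(36.92/22.04) = 4.85. The length is 1.80 mm³, and 1.80/25 = 7.2%.
- SD 5.0: 4.08 and 6.47. The length is 2.40 mm³, or 9.6%.
- The stated 8% and 11% come from the printed table. Averaging n=30 and n=40 gives (2.15 + 1.77)/2 = 1.96 mm³ (7.8%) and (2.87 + 2.37)/2 = 2.62 mm³ (10.5%).

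The printed entries do not follow the footnote. At n=30, SD 3.75, the footnote gives [3.01, 4.97] and the table prints [3.11, 5.26]. All printed values are matched to within 0.01 by keeping m−1 in the numerator but taking chi-square df of n−1 (n=10 to 30) or n (n=40 to 60).

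**2. Coverage under the plan's assumptions.** Differences are normal, with one lesion per carotid patient, two per femoral patient and r=0.5. The interval is for the lesion-level SD, and patients are resampled. Coverage does not depend on the SD chosen. The ranges below span separate simulations of 2,500 to 8,000 data sets with 800 to 1,500 resamples. The Monte Carlo standard error at 90% coverage with 2,500 data sets is √(0.9 × 0.1/2,500) = 0.6 points.

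| Patients (carotid + femoral) | Percentile | Basic | BCa | Log-SD t | Chi-square, footnote df |
|---|---|---|---|---|---|
| 25 + 10 | 89% | 91% | 91% | 93–94% | 96% |
| 55 + 20 | 92% | 93% | 93% | about 94% | 96% |
| 0 + 10 (sites not pooled) | 79–80% | 85% | 84% | 93% | 97% |

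The log-SD t interval is exp[log(SD) ± t × SE], where SE is the patient-bootstrap standard error of log(SD) and t has patients minus 1 df. Resampling lesions instead of patients does not rescue the ordinary intervals (88–91% at 25 + 10, 80–84% at 10 femoral).

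**3. Direction.** At 25 + 10, about 10.3% of percentile intervals lie wholly below the true SD, against a nominal 2.5%, and about 1% lie above. With 10 femoral patients, 19.7% lie below.

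**4. Length.** At 25 + 10 the mean lengths are 0.402 SD (percentile), 0.44 SD (log-SD t) and 0.47 SD (chi-square). The log-SD t interval is therefore 0.44/0.402 = 1.09 times the percentile length; at 10 patients the ratio is about 1.35. As a share of mean volume, its expected length at 25 + 10 is 0.44 × 15% = 6.6% and 0.44 × 20% = 8.8%.

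**5. Departure from normality.** The documents give no tail shape, so t errors with 5 df are an assumption. At 25 + 10, coverage falls to about 82% (percentile), 84% (basic) and 86% (BCa). The log-SD t interval covers about 87–88%. The chi-square interval covers about 81–83%, because its length does not respond to heavy tails.

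**The case against.** A reader might infer that the planned interval itself covers only 89–91%. The documents do not support that: Section 8.1 names no bootstrap type, and those figures belong to the percentile, basic and BCa versions. A log-scale normal bootstrap covers about 92% at 25 + 10 and 89% at 10 femoral patients. A studentised log-scale bootstrap covers about 94% and 93%, though its mean length with 10 patients is about 1.26 SD. The interval proposed below also uses a bootstrap standard error, so the present wording already permits it.

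The 79–85% range is also conditional. It arises only if the site plots differ, and the sizing assumes pooling. Thirty-five is a floor, and near 75 patients the shortfall shrinks to two or three points.

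Nor does sizing on a closed-form interval and reporting a bootstrap one invalidate the sample size. That is common practice, and here the stated 8% and 11% are longer than either interval would give. Aim I sets no acceptance limit for precision, so no pass or fail decision turns on this interval. Section 8.1 also looks for heteroscedasticity and plots a precision profile, so one pooled SD is not its only summary.

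All of this stands. What remains is that the text leaves open a choice worth several points of coverage in a primary result, that the ordinary choices err in the device's favour, and that a better interval is available at little cost.

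**Conclusion.** The concern holds as a gap in specification with a measurable consequence. If an ordinary bootstrap interval is used at 25 + 10 patients, a nominal 95% CI for precision delivers about 89–91%, and at 10 unpooled femoral patients about 79–85%, with most misses on the low side. These figures rest on Section 8.1's assumptions of normality, r=0.5 and its lesion counts. Heavier tails would make every interval worse. Point estimates and the number of patients are unaffected. Separately, Table 5 disagrees with its own footnote; that error overstates the expected length, so it does not imply too few patients.

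**What to change.** In Section 8.1, replace the bootstrap sentence with a statement that the 95% CI for the SD is computed on the log scale, using a standard error from resampling patients (all lesions of a patient kept together) and a t quantile on patients minus 1 df, and then exponentiated. State the number of resamples and that the percentile interval will not be used.

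Do not name the chi-square interval as a fallback. It does well only under normality, which is hard to judge from 45 lesions.

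Recompute Table 5 and the expected lengths in the text for the interval to be reported (about 6.6% and 8.8% at 25 + 10 under normality). If the chi-square table is kept for planning, make its entries follow its footnote and change the n=35 lengths to 7.2% and 9.6%.

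The cost is a sentence, a revised table, and intervals about 9% longer than percentile ones at 35 patients and about 35% longer at 10. No extra patients are needed. Coverage still stays slightly below 95% under normality, and at about 87–88% with the assumed t5 errors at 25 + 10, so the report should call the level approximate.

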### 8.1 Aim I

The first study aim is to estimate the bias and precision of each of the following functional analytes, which will be measured for each target lesion by both vascuCAP™ and histopathology:

- a. Plaque lipid
- b. Plaque fibrosis
- c. Plaque inflammation
- d. Intra-plaque hemorrhage burden and confidence.
- e. Plaque vascular leak
- f. Calcification

For each of these functional analytes, three measurements will be evaluated for a total of 18 measurements per target lesion: volume in mm^3, and degree and uniformity both measured on a three-point ordinal scale. The same measurements will be taken via histopathology, where the volume of each analyte will be measured using the same units (i.e. mm^3); however, degree and uniformity are graded subjectively on histopathology by the pathologist.

We anticipate that each patient will have at least one target lesion and some patients, especially the PAD patients, will have two target lesions, on average. There will be no replicate measurements (i.e. all of the measurements are obtained objectively by the algorithm so multiple runs should not produce different results).

For volume measurements for each analyte for each site (i.e. neck and leg), we will plot the value measured by histopathology vs. the difference between the value measured by vascuCAP™ and the value measured by histopathology. Any analyte not measurable will also be indicated on the plot using a different plotting character. The resulting plot will be inspected visually for the following:

1. Limits of vascuCAP™'s quantitation;
2. Associations between the magnitude of the histopathology measurement and bias; and
3. Associations between the magnitude of the histopathology measurements and heteroscedasticity in the vascuCAP™ measurements.

If the plots of carotid and femoral endarterectomies have similar distributions, then the data from these sites will be pooled; otherwise, separate analyses will be performed.

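### The Aim I precision profile is defined on raw vascuCAP readings, so it mixes true lesion-size spread into device error; it should be built on residuals

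*Combined protocol and SAP*

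**What the plan says.** All of this is in section 8.1 (Aim I) of the combined protocol and SAP, where X is the vascuCAP volume and Y the histopathology volume.

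- Overall precision: "The precision of the vascuCAP™ measurements will be estimated by the standard deviation" of Y − X about d̄, which "is the sample mean of the differences". It has a bootstrap 95% CI.
- Bias profile: a "plot of bias of measurements for various ranges of histopathology values vs. the histopathology value".
- Precision profile: a "plot of standard deviation of vascuCAP™ measurements from patients with similar histopathology values vs. the histopathology value". Nothing is subtracted from the readings.
- Both profiles are offered "as visual summaries of vascuCAP™ performance for the bias and precision components, respectively".
- Repeat readings: "There will be no replicate measurements".

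No range width, number of ranges or minimum count is given for either profile.

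**The concern.** A precision profile should show how device error changes with the size of the quantity measured. A reader would expect this one to break the overall precision figure down by volume. As worded it does not, because the overall figure is based on differences and the profile on raw readings.

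Without replicates, the readings in one range come from different lesions with different true volumes. Their SD therefore has two parts: device error, and real variation in lesion size carried through the slope. The second part grows with the width of the range. The profile then overstates imprecision, its shape depends partly on how the ranges are cut, and a device with flat error can appear to have error that varies with volume. Phase two results go into the 510(k) application, so the display should show what its name says.

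**Working it through.** **Plan's own figure.** The plan states no value for the profile, so there is none to reproduce.

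**Inputs from section 8.1.**
- Mean volume 25 mm³; volumes assumed normal.
- Precision 10–20% of volume; Table 4 uses SDs of 2.5, 3.75 and 5.0 mm³ (15% × 25 = 3.75).
- Phase two minimum: 25 carotid patients × 1 lesion + 10 PAD patients × 2 lesions = 45 lesions.

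**Assumptions, because the documents give no figure.** Range widths of 2 to 20 mm³; between-lesion SD of true volume of 5 to 12.5 mm³. Histopathology is taken as truth, as the plan does.

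**Step 1: formula.** Let X = a + bY + e within a range. Then

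- SD(X) = √[Var(e) + b² Var(Y in range)]
- SD(X − Y) = √[Var(e) + (b − 1)² Var(Y in range)]
- SD(residual of X on Y) = √Var(e)

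For lesions spread evenly over width w, Var(Y in range) = w²/12.

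**Step 2: evenly filled ranges, b = 1.** For w = 10: √(3.75² + 100/12) = √(14.06 + 8.33) = 4.73.

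| Width (mm³) | w²/12 | SD of readings, error SD 3.75 | Overstatement | Overstatement for error SD 5.0 to 2.5 |
|---|---|---|---|---|
| 2 | 0.33 | 3.79 | 1% | 1–3% |
| 5 | 2.08 | 4.02 | 7% | 4–15% |
| 10 | 8.33 | 4.73 | 26% | 15–53% |
| 20 | 33.33 | 6.88 | 84% | 53–152% |

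**Step 3: can the ranges be narrow?** Take 45 lesions, normal with mean 25 and SD 10. A 2 mm³ range centred on the mean holds about 45 × 0.080 = 3.6 lesions, and a 5 mm³ range about 45 × 0.197 = 8.9. Ranges away from the centre hold fewer. If neck and leg are not pooled, there are about 25 and 20 lesions per profile. Ranges with enough lesions to estimate an SD must be fairly wide, above all at the ends.

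**Step 4: simulation at the phase two minimum.** 20,000 data sets of 45 lesions, five equal-count ranges of 9, b = 1. Overstatement from the smallest to the largest range:

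| Volume SD | Error constant at 3.75 | Error 15% of volume |
|---|---|---|
| 5 | 19, 3, 3, 3, 19% | 33, 4, 3, 3, 11% |
| 10 | 52, 12, 10, 12, 61% | 150, 19, 9, 9, 29% |
| 12.5 | 51, 19, 14, 19, 87% | 201, 32, 14, 12, 36% |

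With SD 10 and constant error, the profile reads 5.70, 4.22, 4.11, 4.23, 6.06 for a device whose error SD is 3.75 throughout, which is a U shape made by the ranges. Negative simulated volumes were reflected to positive, which lowers the first range. Exact truncated-normal variances give equal ends: 60% for SD 10 and 85% for SD 12.5.

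**Step 5: proportional error, equal 10 mm³ ranges.** Within a range centred at c, the error variance is 0.15² × (c² + 8.33).
- c = 5: error SD √0.75 = 0.87; SD of readings √(0.75 + 8.33) = 3.01; +248%.
- c = 25: 3.77 becomes 4.75; +26%.
- c = 45: 6.76 becomes 7.35; +9%.

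**Step 6: which replacement works?** At b = 1, both differences and residuals return 3.75. Away from b = 1, differences do not. With b = 0.3, normal volumes of SD 10 and the top quartile, SD(X − Y) is 5.09 and SD(X) is 4.03 against a true 3.75. The residual SD is 3.75.

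**The case against.** The strongest reply is that nothing formal rests on the profile. The plan calls it a visual summary. The overall precision estimate, its bootstrap CI and the coverage probability all use differences between the two methods. This stands, and it limits the severity.

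Second, the wording may be shorthand: the preceding paragraph defines precision through differences, so the profile could mean that estimator within ranges. This is possible, but the sentence names the readings, and an analyst following it would compute their SD.

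Third, in a narrow enough range the SD of readings is a legitimate precision profile. That is true at 2 mm³. A 20 mm³ range is hardly similar: 15–35 mm³ holds about 58% of lesions if volumes have SD 12.5. But about 45 lesions do not allow very narrow ranges, and the plan sets no rule.

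Three stronger readings are tempting and are not supported.

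- A reader might infer that large plaques are affected most. That needs skewed volumes and ranges that widen at the top. With lognormal volumes (CV 0.8) and quartile ranges, the top range is overstated by 525% with constant error. With the same skewed volumes, 15% proportional error and equal-width ranges, the figures are 187% in the lowest range and 13% in the highest. The plan assumes normal volumes and sets no ranges. If error is proportional to volume, as its precision assumption reads, the smallest plaques have the largest relative overstatement.
- A reader might infer a wrong limit of quantitation or a false finding of heteroscedasticity. Section 8.1 assigns both to another plot, of the vascuCAP-minus-histopathology difference against histopathology, which is inspected for "Associations between the magnitude of the histopathology measurements and heteroscedasticity in the" vascuCAP measurements. The range used for the linear model also follows from that plot.
- A reader might infer needless stratification. The plan says only that bias and "precision may need to be reported in strata based on the magnitude of the histopathology volume"; it does not tie that choice to the profile.

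**Conclusion.** The point holds as a moderate correction to one reported display. As written, the profile overstates device error whenever the slope is not zero and a range has width. The excess depends on range width, slope and the spread of volumes in the range, none of which the documents fix. At slope 1 and error SD 3.75 mm³ it runs from about 1% at 2 mm³ to 26% at 10 mm³ and 84% at 20 mm³. With normal volumes, constant error and equal-count ranges, the result is a false U shape. With proportional error, the relative excess is greatest at the small end. Any one percentage is illustrative; the direction and the mismatch with the plan's own definition of precision are not.

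**What to change.** In section 8.1, define the precision profile as the SD, within each histopathology range, of the residuals from the regression of vascuCAP (dependent) on histopathology (independent). A smooth of the squared residuals against histopathology volume would also serve, and needs no ranges.

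Name the direction explicitly. The text makes vascuCAP (X) the dependent variable but prints E(Y|X) = β₀ + β₁X, and residuals from the printed line would be histopathology residuals. Residuals are preferable to plain differences because they stay correct when the slope is not 1.

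State the ranges, use the same ones for the bias and precision profiles, and set a minimum lesion count per range.

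The cost is a sentence or two of wording and a small change to the plotting code, with no new data. It should be settled before phase two is analysed.

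### Section 8.1 gives no interval form and no boundary rule for the coverage probability, so once every lesion lies within d0 its 95% CI is undefined or, in the common form, reads 100% (100–100%)

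*Combined protocol and SAP*

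**What the plan says.** For the volume measurements, Section 8.1 defines CP as the probability that the absolute vascuCAP–histology difference is below d0. "We will plot the CP for a range of values for" d0, it says, without giving the limits of that range. On uncertainty it says only that "95% CIs for the CP and ROC area will be constructed using methods for clustered binary data [14] and clustered ROC data [15], respectively".

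After Table 5 the same approach is applied to the degree and uniformity grades at d0 of 0 and 1: "95% CIs for the CP will be constructed using methods for clustered binary data [6"]. Reference 6 in the list is a document on tissue classification and reference 14 is the clustered-binary paper, so the second citation looks like a slip.

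Neither place names the interval (estimate ± SE, Wilson, exact, logit) or says what to do when observed CP is 0% or 100%. The precision reasoning in Tables 4 and 5 covers bias and SD only.

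**The concern.** A CP curve plotted against d0 climbs to 1. Once d0 exceeds the largest observed difference, every lesion counts as covered. A method that estimates variance from between-patient variation in a covered/not-covered indicator then has no variation to work with. The analyst must improvise a rule after seeing the data or print an interval of zero width.

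Phase two supplies the performance results for the 510(k) filing (Sections 4 and 8), and Section 8.1 calls the volume measurements the most critical. An interval of 100–100% from a few dozen lesions would claim certainty that the data cannot give, and the error is always in the flattering direction.

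**Working it through.** **Inputs, all from Section 8.1 unless marked**
- Phase two: "In phase two we plan to recruit at least the minimum of 35 (25 carotid artery patients and 10 PAD patients").
- Phase one: "We plan to recruit 75 patients (55 carotid artery patients and 20 PAD patients) in phase one".
- Cluster sizes: "carotid artery patients contribute one target lesion each, while PAD patients contribute two target lesions each". So 25 + 2×10 = 45 lesions in phase two and 55 + 2×20 = 95 in phase one.
- Correlation: "target lesions from the same patient are moderately correlated", r = 0.5.
- Distribution: "the volume measurements are normally distributed". I take the differences as normal with zero bias (assumption).
- SD: 15% of 25 mm³ = 3.75 mm³, the middle of the plan's range. It cancels once d0 is expressed in SD units.
- Interval form: estimate ± 1.96 clustered SE (assumption).
- True CP: 0.90 to 0.99 (assumption, since no d0 range is given).

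**The plan's nearest figure.** No precision is stated for CP. Table 4 uses the same inputs. At n = 40, m = 0.75×40 + 0.25×40×(2/1.5) = 43.3, and t × 3.75/√43.3 = 1.15, as printed. All 18 cells reproduce within 1.4%.

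**Mechanism.** Let patient i have x_i covered lesions out of n_i, with C patients, N lesions and observed proportion p. The empirical clustered variance is v = [C/(C−1)] Σ(x_i − n_i p)²/N², and the design effect is N v/[p(1−p)]. If every lesion is covered, p = 1 and x_i = n_i, so each residual is 0. Then v = 0 and the design effect is 0/0. This is certain for every d0 above the largest observed difference. A Wilson or exact interval on an effective sample size also needs that design effect, so it too requires a stated rule.

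**How often, in phase two (25 + 10).** P(all covered) = π^25 × q^10, where π is the true CP and q is the probability that both lesions of a PAD patient are covered (bivariate normal, r = 0.5, numerical integration).
- π = 0.95 (d0 = 1.96 × 3.75 = 7.35 mm³): q = 0.909; 0.277 × 0.386 = 0.107.
- π = 0.98 (d0 = 2.326 × 3.75 = 8.72 mm³): q = 0.963; 0.603 × 0.683 = 0.412.

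A zero-width interval at 100% always misses a true CP below 1, so coverage cannot exceed 1 − 0.107 = 89% or 1 − 0.412 = 59%. Other correlations change little: 87–90% at 0.95 and 55–60% at 0.98, from independence to a correlation of 0.5 in the indicator itself.

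**Simulated coverage of estimate ± 1.96 SE (40,000 trials per setting)**

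| True CP | 25 + 10 | 55 + 20 |
|---|---|---|
| 0.90 | 93% | – |
| 0.95 | 89% | 88% |
| 0.97 | 74% | 94% |
| 0.98 | 58% | 85% |
| 0.99 | 36% | 60% |

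At 25 + 10, intervals with at least one uncovered lesion cover more than 99% for true CP of 0.95 to 0.99, so nearly all the loss is the all-covered case. The lower limit exceeds the truth in 10.6% (0.95) and 41.6% (0.98) of trials; the upper limit falls below it in 0.3% and 0.1%.

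At 55 + 20 and true CP 0.95, the all-covered case arises in only 0.9% of trials (1 − 0.991). There the shortfall is the ± SE form itself: non-degenerate intervals cover about 89%.

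If the beds are analysed separately, which Section 8.1 allows, the ceilings at 0.95 are 1 − 0.277 = 72% for 25 carotid patients and 1 − 0.386 = 61% for 10 femoral patients.

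**With a repaired interval.** Across the settings tested, a beta interval on effective counts covers 97–99.8% and a Wilson interval 91–98%. With all lesions covered, the exact two-sided lower limit is 0.025^(1/m). The Table 4 formula at n = 35 gives m = 26.25 + 11.67 = 37.9 and a limit of 90.7%. Applied to the actual 25 + 10 mix, m = 25 + 10×(2/1.5) = 38.3 and the limit is 90.8%. Counting 45 independent lesions gives 92.1%.

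**The case against.** The strongest reply is that the plan never commits to estimate ± 1.96 SE. A Wilson or exact interval on an effective sample size fits the same sentence and covers about 93–99% at 25 + 10. This stands. A reader might infer that the planned CI covers only about 57–88%, but the documents do not support that. Those figures belong to an assumed form, the minimum phase-two size and true CP of about 0.95 to 0.98. Coverage is about 93% at 0.90, and Section 4 allows up to 75 patients in phase two.

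A reader might also infer that intervals just below 100% are far too short. At 25 + 10 they are not.

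Three further points stand. CP is reported in addition to bias and precision, with no target, acceptance limit or sample size resting on it, and nothing in the plan says that the top of the curve matters most. A 100–100% interval would look odd to most readers. And r = 0.5 is the plan's correlation for volumes; under this model the covered/not-covered indicator has a correlation of only about 0.14 at CP 0.95 and 0.11 at 0.98, so using 0.5 for the fallback is a conservative choice and not something that the plan dictates.

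None of this supplies the missing boundary rule, which every interval form needs.

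**Conclusion.** The point holds as a specification gap. Section 8.1 leaves the CP interval undefined for every d0 above the largest observed difference, and the common ± SE form would print 100% (100–100%) there. At 25 + 10 patients, with r = 0.5, normal differences and no bias, that occurs in about 11% of trials where true CP is 0.95 and 41% where it is 0.98.

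The coverage figures are conditional on the ± 1.96 SE form; the zero variance and 0/0 design effect hold for any method that estimates variance from between-patient variation.

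For degree and uniformity, the same gap exists at d0 = 1, which under the strict inequality means exact agreement. Its size was not calculated, and nothing shows that agreement on subjective grades would approach 100%. At d0 = 0 the strict inequality makes CP equal to 0 by definition; that is a separate error in the definition, which no choice of interval can repair.

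The change is worth making before phase-two data are seen. It alters no sample size and no stated decision.

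**What to change.** In Section 8.1, for the volume CP:
- State that the 95% CI is a Wilson or beta (Clopper–Pearson type) interval on cluster-adjusted effective counts, with the design effect floored at 1.
- State that when observed CP is 0 or 1, a prespecified effective sample size is used. The Table 4 footnote formula is one conservative option: about 38 for 25 + 10 patients, which gives a lower limit of about 91% when all 45 lesions are covered.
- State the range of d0 to be plotted.

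In the paragraph after Table 5, apply the same interval to CP at d0 = 1, correct the definition so that d0 = 0 yields a meaningful quantity (for example, a non-strict inequality, which makes d0 = 0 exact agreement and d0 = 1 agreement within one grade), and check the citation.

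The cost is wording only. Intervals near 100% become wider, and the beta form is somewhat conservative. Wilson is shorter but falls a few points below 95% in some settings.
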